6.2 Treatment

The treatment period begins on the day the subject receives the first dose of study drug (Cycle 1 Day 1) through the point at which the investigator determines that the subject will be permanently discontinued from study drug. Cycle 1 Day 1 must occur within approximately 30 days after the subject has signed the main ICF.

Subjects will have regularly scheduled study visits on Day 1 of every cycle \pm 3 days (after Cycle 1). Additional visits will be required on Day 2 and 3 (for subjects enrolled in Phase 1 only) and at Day 8 (all subjects) of Cycles 1 and 5. During study visits, the subject will have clinical and laboratory assessments as outlined in Table 7 and Table 8. At certain study visits as indicated in [Section 7.7](#) and [Section 7.8](#), subjects will have PK, PD, and biomarker samples obtained (see Table 10 and Table 11). Toxicities will be monitored continuously and will be graded using the NCI CTCAE v5.0 criteria.

During Cycle 1 subjects will be required to stay at the study site for safety observation for 4 hours post end of infusion. At Cycle 1, vital signs (blood pressure, pulse, respiratory rate, and body temperature) will be collected pre-dose, at end of infusion (+10 minutes), and every 60 minutes (\pm 10 minutes) thereafter. On Day 1 of all subsequent cycles subjects will be required to be observed for a minimum of 1 hour post end of infusion or per PI

discretion if indicated. After cycle 1, vital signs (blood pressure, pulse, respiratory rate, and body temperature) will be assessed pre-dose and at end of infusion (+10 minutes).

It is recommended that the subject does not leave the site for any reason during the safety observation period. During the safety observation period, subjects will be assessed for the onset of acute AEs.

6.3 End of Treatment

When the subject permanently discontinues study drug, the EOT visit should be conducted. If the EOT visit coincides with a regular study visit, then the EOT evaluations will supersede those of that scheduled visit, and the data should be entered in the EOT visit in the eCRF. The subject should be encouraged to return for the follow-up visit(s).

6.4 Follow-up

6.4.1 Safety Follow-up

The safety follow-up period is the interval between the EOT visit and the scheduled follow-ups, which should occur 30 days (+ 7 days) and 90 days (+ 7 days) after the EOT visit (or after the last dose of study drug if the EOT visit was not performed). AEs and SAEs must be reported up until at least 90 days after the last dose of study drug, the date of the last follow-up, or until toxicities resolve, return to baseline, or are deemed irreversible, whichever is longer. The safety follow-up must be performed before any new systemic anticancer therapy is started regardless of whether it occurs before the end of the 30- or 90-day safety follow-up period; it can, in fact, be done on the same day provided it is done before the start of the new systemic anticancer therapy (e.g. prior to dosing).

6.4.2 Disease Status Follow-up

Subjects who discontinue study drug for a reason **other than** disease progression will move into the disease status follow-up period and should continue to be assessed every 8 weeks (56 days \pm 7 days) for the first 6 months and then every 12 weeks (84 days \pm 7 days) thereafter, by radiologic imaging to monitor disease status. Every effort should be made to collect information regarding disease status until the earliest of the following:

- Withdrawal of consent
- The start of a new systemic anticancer therapy
- Documented disease progression
- Death
- End of the study

6.5 End of Study

The end of the study will occur when all subjects have completed the last study follow-up visit or have discontinued study drug and have completed applicable follow-up assessments.

Additionally, subjects will be considered as having completed the study if they meet any of the following criteria:

- Subject dies and a date of death is available
- Subject is known to have died; however, the date of death cannot be determined
- Consent is withdrawn for any further contact to this study (Every reasonable effort should be made to determine the reason a subject withdraws prematurely, and this information should be recorded)
- The study is terminated by the sponsor
- The study is terminated by the IRB or local health authority

6.6 Unscheduled Visits

Unscheduled study visits may occur at any time if medically warranted. Any assessments performed at those visits should be recorded in the eCRF.

7 CONDUCT OF STUDY ASSESSMENTS AND PROCEDURES

Individual study procedures are described in detail below. It may be necessary to perform these procedures at unscheduled timepoints if deemed clinically necessary by the investigator. Furthermore, additional evaluations/testing may be deemed necessary for reasons related to subject safety. In some cases, such evaluation/testing may be potentially sensitive in nature (e.g., HBV, HCV), and thus local regulations may require that additional informed consent be obtained from the subject. In these cases, such evaluations/testing will be performed in accordance with those regulations. Subjects of childbearing potential must agree to take appropriate measures to avoid pregnancy in order to participate in the study.

7.1 Administration of Informed Consent Form

Valid informed consent must be obtained from the subject before conducting any study-specific procedures using an ICF approved by the IRB/IEC. The ICF should contain all elements required by ICH E6 and describe the nature, scope, and possible consequences of the study in a manner that the subject can understand. Local and institutional guidelines for ICF content and administration must be followed; the original signed ICF must be retained by the investigator, and a copy of the signed ICF must be provided to the study subject. The informed consent process for each subject must be documented in writing within the subject source documentation.

7.2 Demography and Medical History

7.2.1 Demographics and General Medical History

Demographic data and a complete medical and medication history will be collected at screening by the investigator or qualified designee and will include date of birth, race, ethnicity, medical and surgical history, and current illnesses. Medical history will include relevant medical or surgical treatment within the last 10 years that are considered to be clinically significant by the investigator.

7.2.2 Disease Characteristics and Treatment History

A disease-targeted medical and medication history will be collected at screening. Details regarding the subject's malignancy under study including date of diagnosis, initial and current cancer stage, primary tumor histology, and prior treatments including systemic, radiation, and surgical procedures will be recorded.

7.3 Prior and Concomitant Medications and Procedures

Prior and concomitant medications and procedures will be reviewed to determine subject eligibility. All concomitant medications and measures must be recorded in the eCRF, and any medication received, or procedure performed within 30 days before the first dose of study drug and up to the end of the follow-up phase of the study will be recorded in the eCRF. The medication record will be maintained after signing the ICF to document concomitant medications, including any changes to the dose or regimen. Concomitant medications include any prescription, over-the-counter, non-drug or natural/herbal preparations taken or administered during the study period. Concomitant treatments and/or procedures that are required to manage a subject's medical condition during the study will also be recorded in the eCRF.

7.4 Poststudy Anticancer Therapy Status

The investigator or qualified designee will review all new systemic anticancer therapy initiated after the last dose of study drug. If a subject initiates a new systemic anticancer therapy within 30 to 90 days after the last dose of study drug, the 30-day or 90-day safety follow-up should occur before the first dose of the new systemic anticancer therapy.

7.5 Safety Assessments

7.5.1 Adverse Events

Adverse events will be monitored from the time the subject signs the ICF. Subjects will be instructed to report all AEs during the study and will be assessed for the occurrence of AEs throughout the study. In order to avoid bias in eliciting AEs, subjects will be asked general, nonleading questions such as "How are you feeling?" All AEs (serious and nonserious) must be recorded on the source documents and eCRFs regardless of the assumption of a causal relationship with the study drug. The definition, reporting, and recording requirements for AEs are described in [Section 8.1](#).

7.5.2 Physical Examinations

7.5.2.1 Comprehensive Physical Examination

Physical examinations must be performed by a medically qualified individual such as a licensed physician, physician's assistant, or an advanced registered nurse practitioner, as local law permits. ECOG performance status should be assessed.

The comprehensive physical examination will include assessment(s) of the following organ or body systems: skin; head, eyes, ears, nose, and throat; thyroid; lungs; cardiovascular system; abdomen (liver, spleen); extremities; and lymph nodes, as well as a brief neurological examination. The screening physical examination should also include a measurement of height.

Clinically notable abnormalities that are considered clinically significant in the judgment of the investigator are to be reported as AEs.

7.5.2.2 Targeted Physical Examination

The targeted physical examination will be a symptom-directed evaluation conducted by the investigator or a medically qualified designee. The targeted physical examination will include assessment(s) of the body systems or organs, as indicated by subject symptoms, AEs, or other findings. Clinically notable abnormalities that are considered clinically significant in the judgment of the investigator are to be reported as AEs.

7.5.3 Vital Signs and Weight

Vital sign measurements include blood pressure, pulse, respiratory rate, and body temperature. Blood pressure and pulse will be taken with the subject in the recumbent, semi recumbent, or sitting position after 5 minutes of rest. At Cycle 1, vital signs (blood pressure, pulse, respiratory rate, and body temperature) will be collected pre-dose, at end of infusion (+10 minutes), and every 60 minutes (\pm 10 minutes) thereafter. After cycle 1, vital signs (blood pressure, pulse, respiratory rate, and body temperature) will be assessed pre-dose and at end of infusion (+10 minutes). Subjects will also be assessed for the onset of acute AEs.

Weight will also be assessed at each study visit. Clinically notable abnormalities that are considered clinically significant in the judgment of the investigator are to be reported as AEs.

7.5.4 Electrocardiograms

All 12-lead ECGs will be performed with the subject in a recumbent or semirecumbent position after 5 minutes of rest and should not be performed within at least 15 minutes after a blood collection. All 12-lead ECGs should be acquired using an ECG system with analysis and printing capabilities. ECG assessments will be done as single assessments as per Table 12.

A single 12-lead ECG should be performed at Screening and EOT for all subjects.

On Day 1 of Cycles 1 and 5, ECGs will be collected in conjunction with PK samples at the following timepoints: pre-infusion and post-infusion. Additional ECGs should be performed per PI discretion if any clinically significant abnormal findings are noted or as indicated.

The 12-lead ECGs readings will be interpreted by the investigator, or qualified designee at the site to be used for immediate subject management. The decision to include or exclude a subject or withdraw a subject from the study based on a locally analyzed ECG flagged as "Abnormal, Clinically Significant" is the responsibility of the investigator, in consultation with the medical monitor, as appropriate. Clinically significant abnormal findings before signing consent should be recorded as medical history. Clinically significant abnormal findings after signing consent should be recorded as an AE. For any subjects with clinically significant abnormalities, ECGs may be conducted more frequently than the protocol-required timepoints per PI discretion.

Table 12: Timing of Electrocardiograms

ECG Schedule ^c		Timing of Sample		
Study Visit	Any Time	Pre-infusion	Post-infusion	
Screening	X			
C1D1		X ^a	X ^b	
C5D1		X ^a	X ^b	
EOT	X			

^aECGs should be conducted within 30 minutes prior to the PK blood draw.

^bECGs should be started 15 to 30 minutes after the PK sample is drawn.

^cAdditional ECGs should be performed per PI discretion if any clinically significant abnormal findings are noted or as indicated.

7.5.5 Laboratory Assessments

A laboratory local to the study site and subject will perform all clinical laboratory assessments for safety (i.e., blood chemistries, hematology assessments, coagulation tests, endocrine function, and urinalysis). The investigative site will enter the laboratory results into the eCRF and select the laboratory name so that the laboratory normal ranges will populate. All local laboratory assessments should be performed using standard procedures on the days indicated in Table 7 and Table 8. Table 9 lists the specific laboratory analytes required for each test. Additional testing may be required by the sponsor based on emerging safety data. Additional tests may also be performed if clinically indicated.

Serum chemistry, hematology, coagulation, urinalysis, and endocrine function tests must be performed during screening period and on Cycle 1 Day 1.

Laboratory samples collected on Cycle 1 Day 1 must be performed before study drug administration. Cycle 1 Day 1 safety lab results should be reviewed by the investigator or qualified designee and found to be acceptable prior to study drug administration.

After Cycle 1, pre-infusion laboratory procedures can be conducted up to 72 hours before study drug administration, and results should be reviewed by the investigator or qualified designee and found to be acceptable before a new cycle of treatment is initiated.

7.5.5.1 Pregnancy Testing

A local laboratory serum pregnancy test will be required for all women of childbearing potential during screening and at the EOT visit. The serum pregnancy test performed at screening must be performed within 72 hours before the first dose of study drug. Urine pregnancy tests will be performed for women of childbearing potential locally as outlined in Table 8, as medically indicated, or per country-specific requirement. If a urine pregnancy test is positive, then the results should be confirmed with a serum pregnancy test. If the serum pregnancy test is negative after a urine test was positive, then the investigator will assess the potential benefit/risk to the subject and determine whether it is in the subject's best interest to resume study drug and continue participation in the study.

7.5.5.2 Hepatitis Screening Tests

Hepatitis screening assessments will be performed at the screening visit (Table 8) to rule out hepatitis infection; required analytes are shown in Table 9. Generally, hepatitis tests should be performed early in the screening process due to the length of time needed to obtain the results. Additional tests may be performed if clinically indicated.

7.6 Efficacy Assessments

7.6.1 Modified RECIST v1.1 Assessment of Disease

Modified RECIST will be applied by the site as the primary measure for assessment of tumor response and as a basis for protocol guidelines related to disease status (e.g., discontinuation of study therapy). As noted in [Section 1.3.4](#), RECIST v1.1 has been adapted to account for the unique tumor responses seen with immunotherapy ([Wolchok et al., 2009](#)).

If radiologic imaging shows progressive disease, then tumor assessments should be repeated at a minimum of 4 weeks, but no later than 6 weeks later to confirm progression, with the option of continuing treatment while awaiting radiologic confirmation of progression. Table 13 provides instructions on how to proceed with treatment based on the subject's clinical status once the initial scan showing radiologic evidence of progression is observed.

Subjects may receive treatment while waiting for confirmation of progression if they are clinically stable as defined by the following criteria:

- Absence of clinically significant signs and symptoms (including worsening of laboratory findings) consistent with disease progression
- No decline in ECOG performance status
- Absence of rapid progression of disease
- Absence of progressive tumor at critical anatomic sites (such as spinal cord compression) requiring urgent alternative medical intervention

Table 13: Imaging and Treatment After First Radiographic Evidence of Progressive Disease

	Clinically Stable		Clinically Unstable	
	Tumor Imaging	Treatment	Tumor Imaging	Treatment
First radiologic evidence of progression	Repeat imaging 4-6 weeks to confirm progression	May continue study treatment at the investigator's discretion while awaiting confirmatory tumor imaging	Repeat tumor imaging 4-6 weeks to confirm progression per physician discretion only	Discontinue treatment
Repeat scan confirms progression	No additional tumor imaging required	Discontinue treatment	No additional tumor imaging required	N/A

Repeat scan shows SD, PR, or CR	Continue regularly scheduled tumor imaging assessments	Continue study treatment at the investigator's discretion	Continue regularly scheduled tumor imaging assessments	May restart study treatment if condition has improved and/or clinically stable per investigator's discretion
---------------------------------	--	---	--	--

SD = stable disease; PR = partial response; CR = complete response.

As noted above, if disease progression is observed, then the study site may elect to continue treatment and repeat imaging at a minimum of 4 weeks, but no later than 6 weeks later, to assess tumor response or confirm progression per mRECIST.

In determining whether or not the tumor burden has increased or decreased, study site investigators should consider all target lesions as well as nontarget lesions. Subjects that are deemed clinically unstable are not required to have repeat tumor imaging for confirmation. If radiologic progression is confirmed by subsequent scan, then the subject should be discontinued from study treatment.

If radiologic progression is not confirmed, then the subject should resume or continue study treatment and have the next tumor imaging according to the protocol schedule (see Table 7). If progression is not confirmed and the subject continues on treatment, then the date of the next scan that documents disease progression (and is confirmed by a second scan at least 4 weeks, but no later than 6 weeks later) will be considered the date of disease progression.

If a subject has confirmed radiographic progression (i.e., 2 scans at least 4 weeks, but no later than 6 weeks apart demonstrating progression) per mRECIST, but the subject is achieving a clinically meaningful benefit, an exception to continue treatment may be considered after consultation with the medical monitor. Clinically stable subjects at the confirmatory scan should also have no further increase in the target lesions, no unequivocal increase in nontarget lesions, and no additional new lesions develop (non-worsening disease progression) to continue study treatment.

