If repeat imaging shows < 20% tumor burden compared with nadir, stable or improved previous new lesion (if identified as cause for initial disease progression), and stable/improved nontarget disease (if identified as cause for initial disease progression), then treatment may be continued or resumed. If repeat imaging confirms disease progression due to any of the scenarios listed below, then subjects will be discontinued from study therapy. However, if a subject has confirmed

radiographic progression (i.e., 2 scans at least 4 weeks but no later than 6 weeks apart demonstrating progression) per mRECIST, but the subject is achieving a clinically meaningful benefit, then an exception to continue treatment may be considered after consultation with the medical monitor. Clinically stable subjects at the confirmatory scan should also have no further increase in the target lesions, no unequivocal increase in nontarget lesions, and no additional new lesions develop (non-worsening disease progression) to continue study treatment.

In determining whether the tumor burden has increased or decreased, site study teams should consider all target lesions as well as nontarget lesions (refer to RECIST v1.1 guidelines).

Scenarios where disease progression is confirmed at repeat imaging include the following:

- Tumor burden remains $\geq 20\%$ and at least 5 mm absolute increase compared with nadir
- Nontarget disease resulting in initial disease progression is worse (qualitative)
- New lesion resulting in initial disease progression is worse (qualitative)
- Additional new lesion(s) are found since the last evaluation

When feasible, subjects should not be discontinued until progression is confirmed. This allowance to continue treatment despite initial radiologic progression considers the observation that some subjects can have a transient tumor flare in the first few months after the start of immunotherapy but with subsequent disease response. Subjects who are deemed clinically unstable are not required to have repeat imaging for confirmation of disease progression.

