2.2.2 Secondary Endpoints

- 1) Assessment of PK of NC762 include individual NC762 concentrations in serum and identification of PK parameters.
- 2) Assessment of antitumor activity/efficacy include objective response (OR) and DCR based on RECIST v1.1, DoR, PFS, and overall survival (OS) as per RECIST v1.1 and mRECIST v1.1
- 3) Tumor biopsy analyses to evaluate downregulation of B7-H4 expression and changes in tumor infiltrating lymphocytes after NC762 treatment.

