7.6.1.1.2 Tumor Imaging During the Study

The first imaging assessment should be performed 8 weeks after the first dose of study drug (during Cycle 4) and then every 8 weeks (56 days \pm 7 days) for 6 months and then every 12 weeks (84 days \pm 7 days) thereafter until disease progression is determined. Imaging assessments may be done more frequently if clinically indicated. **Imaging should not be delayed for delays in cycle starts.** If imaging is delayed, the missed scan should be conducted as soon as possible, and all subsequent scans must remain on schedule (every 8 weeks relative to the first dose of NC762) and should not be adjusted.

Per mRECIST v1.1, response should be confirmed by a repeat radiographic assessment not less than 4 weeks from the date that the response was first documented. The scan for confirmation of response may be performed at the earliest 4 weeks after the first indication of response or at the next scheduled scan, whichever is clinically indicated.

Imaging should continue to be performed until documented disease progression, the start of new systemic anticancer treatment, withdrawal of consent, death, or the end of the study, whichever occurs first. Disease progression should be confirmed at least 4 weeks, but no later than 6 weeks after the first scan indicating progression in clinically stable subjects.

Subjects who have unconfirmed disease progression may continue on treatment until progression is confirmed, provided that they have met the conditions detailed in [Section 7.6.1](#). A central imaging vendor will not be used in this study.

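### The 6-week upper limit inside the definition of confirmed progression can delay or remove the mRECIST PFS and DoR event when the repeat scan is late

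*Combined protocol and SAP*

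**What the plan says.** Section 7.6.1 describes confirmed radiographic progression per mRECIST as "2 scans at least 4 weeks, but no later than 6 weeks apart demonstrating progression". Section 1.3.4 has the same definition: "2 scans at least 4 weeks but no later than 6 weeks apart demonstrating progression".

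Section 7.6.1 also gives the only explicit rule for dating progression under mRECIST: "If progression is not confirmed and the subject continues on treatment, then the date of the next scan that documents disease progression", with the condition "and is confirmed by a second scan at least 4 weeks, but no later than 6 weeks later) will be considered the date of disease" (last word cut). The later scan must therefore meet the same 4-to-6-week condition.

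Other parts of the protocol that bear on the point:

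- **Table 13 (7.6.1)** gives two outcomes for the repeat scan: it confirms progression, or "Repeat scan shows SD, PR, or CR". There is no row for a repeat scan that shows progression after more than 6 weeks.
- **Section 1.3.4** lists the findings that confirm progression at repeat imaging (persisting tumor burden, worse nontarget disease or new lesion, additional new lesions). The list has no time limit.
- **Section 7.6.1.1.2** schedules scans every 56 ± 7 days for 6 months and then every 84 ± 7 days, counted from the first dose. It lets a response be confirmed at any time from 4 weeks on, including at the next scheduled scan.
- **Section 7.6.1** does not require a repeat scan for clinically unstable subjects.
- **Section 2.2.2** lists "DoR, PFS, and overall survival (OS) as per RECIST v1.1 and mRECIST v1.1" as secondary endpoints.
- **Section 9.5.3** determines tumor response by RECIST v1.1 and ends PFS and DoR at the first documented progression or death. It gives no separate rule for the mRECIST versions.

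**The concern.** Four to six weeks is a sensible target for an extra scan. Written into the definition, the upper limit makes the event depend on when the scan was booked. A tumor that still meets the progression criteria at 43 days is at least as good evidence of true progression as one that does so at 28 days, yet only the second counts. Scheduled scans have a ±7-day window; the confirmatory scan has none beyond the 4-to-6-week range itself.

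On the literal wording the effect goes one way. A late repeat scan can only push the mRECIST progression date back or leave the subject without a confirmed date. There is no central imaging vendor, so the sites apply this wording themselves, and section 9.5.3 has no mRECIST rule that would override it. At stake is the comparability of mRECIST PFS and DoR between subjects whose extra scan was on time and those whose scan was late.

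**Working it through.** The plan states no figure that depends on this rule, so there is none to reproduce. The check is day arithmetic plus an illustration.

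**Inputs.** Confirmation interval 4 to 6 weeks = 28 to 42 days (7.6.1, 1.3.4). Scheduled scans every 56 ± 7 days for 6 months, then every 84 ± 7 days, from first dose (7.6.1.1.2).

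**1. A late extra scan.** 6 weeks + 1 day = 43 days; 7 weeks = 49 days. Both exceed 42, so neither confirms.

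**2. The next scheduled scan.** Both scans carry their own ±7-day window around a fixed calendar, so the gap is the nominal interval ± 14 days.

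| Schedule | Nominal gap | Possible gap | Whole-day combinations within 28–42 days |
|---|---|---|---|
| 8-weekly | 56 | 56 − 14 to 56 + 14 = 42 to 70 | 1 of 15 × 15 = 225 |
| 12-weekly | 84 | 84 − 14 to 84 + 14 = 70 to 98 | 0 of 225 |

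The single case is a first scan 7 days late and a second 7 days early, for example Day 63 and Day 105, exactly 42 days apart.

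**3. One record.** Progression on Day 56 and again on Day 99; the subject is clinically stable and stays on treatment.

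- Gap: 99 − 56 = 43 days, so not confirmed on the literal wording.
- The Day 99 scan becomes the next candidate. It needs a further progression scan between Day 99 + 28 = 127 and Day 99 + 42 = 141.
- The Week 16 scan (Day 112 ± 7 = 105 to 119) is too early and the Week 24 scan (Day 168 ± 7 = 161 to 175) too late, so a third scan outside the schedule is needed.
- With it, the date is Day 99 instead of Day 56: 43/56 = +77%. Without it, this pair of scans gives no confirmed date, and the outcome is a still later progression, death or censoring.

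If the second scan is instead the nominal Week 16 visit, the date moves from Day 56 to Day 112 at the earliest.

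**4. Average effect (illustration).** If a share *p* of progressors has a late second scan and each is re-dated by *d* days, the mean date moves by *p* × *d*. For a scan 7 weeks later (*d* = 49): 0.10 × 49 = 4.9 days, 0.25 × 49 = 12.3 days, 0.50 × 49 = 24.5 days.

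A simulation used exponential time to progression with true medians of 60, 90 and 150 days, nominal scans at Days 56, 112 and 168 and then every 84 days, and re-dating either by 49 days or to the next scheduled scan:

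| Assumed late share | Shift in mean date | Shift in median |
|---|---|---|
| 10% | about 5 to 7 days | none |
| 25% | about 12 to 18 days | none |
| 50% | about 24 to 36 days | none at a true median of 60 days; 49 to 84 days at 90 and 150 |

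The late shares and the true medians are assumptions; the documents give neither. Every late subject is re-dated, so stopping treatment, clinical instability, death and censoring are ignored.

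**The case against.** **The text is ambiguous rather than a clear rule that late scans fail.** The untimed list in section 1.3.4 would accept a late scan with persisting growth. Section 7.6.1 also speaks of confirmation by a subsequent scan without an upper limit. Table 13 sets confirmation only against stable disease or response, so it does not place a late progression scan under non-confirmation. The two-scan definition itself sits in a sentence about exceptions for continuing treatment. All of this stands, and it is why the status of such a scan is unclear. It does not remove the problem, because the dating sentence in 7.6.1 carries the same 6-week limit and concerns the event date directly.

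**A reader might infer that the trial's PFS and DoR as a whole are moved later.** The documents do not support that. Section 9.5.3 uses RECIST v1.1 and first documented progression, so those values shift by 0 days. Only the mRECIST versions named in 2.2.2 are exposed. If the first-documented rule were meant for them too, it would contradict 7.6.1, and that has to be resolved in any case.

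**A reader might infer that two scheduled scans can never confirm, or that every subject is affected.** Neither is right. An 8-weekly pair can be exactly 42 days apart, though this is rare. The re-dating sentence applies only to subjects who continue treatment, and clinically unstable subjects need no repeat scan.

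**The endpoints carry little weight.** They are secondary and single-arm, no formal hypothesis test is planned (9.3), and no sample size rests on them. This stands and limits the importance of the point.

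**Conclusion.** The definition and the dating rule in section 7.6.1 contain a 6-week upper limit under which a persisting progression scan at 43 days or later does not confirm. Table 13 and section 1.3.4 leave the status of such a scan unclear. For clinically stable subjects who continue treatment, the mRECIST PFS or DoR event can therefore be dated later, or have no confirmed date.

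For an affected subject the shift is 43 days in the worked record, and nominally 56 or 84 days if the second scan is the next scheduled one. Across the trial the size cannot be known, because it depends on the share of late repeat scans. At assumed shares of 10% and 25% the mean moves by about 5 to 18 days and the Kaplan-Meier median would probably not move. This is a minor point, worth correcting because the correction is cheap and the literal rule errs in one direction.

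**What to change.** For mRECIST endpoint dating only, put one rule in sections 7.6.1 and 9.5.3:

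*Progression is confirmed by any later scan, at least 4 weeks after the first progression scan, that still meets the progression criteria, with no intervening SD, PR or CR, and is dated to that first progression scan. If SD, PR or CR intervenes, the next progression scan starts a new confirmation.*

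The condition on intervening SD, PR or CR is essential. Without it, a subject with pseudoprogression at Week 8, a later response and true progression long afterwards could be dated back to Week 8, against the purpose of section 7.6.1.

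Keep 4 to 6 weeks as the target time for the repeat scan. State in 9.5.3 that first documented progression is the RECIST v1.1 rule and that the mRECIST versions follow the rule above. Reconcile the wording in 1.3.4, 7.6.1, Table 13 and 9.5.3. Some of it also governs treatment after progression; no change to those treatment rules is proposed here.

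Cost: a short text change and no new scans. mRECIST PFS and DoR may come out slightly shorter than under the literal wording.
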